1.10.3 Subgroup analyses

Primary and secondary efficacy analyses will be repeated by subgroup of prior use of any biologics (No/Yes) and by age groups (<18 years old and ≥ 18 years old).

Primary and secondary efficacy endpoints based on week 16 will be repeated by Colchicine subgroup as defined below for crFMF cohort only. Colchicine is defined with ATC code: M04AC01.

Two groups will be defined:

Colchicine negative defined as :

- Colchicine Naïve patients (no colchicine before or after treatment)
- Patient who took colchicine before and stopped before receiving ACZ drug
- Patient who took colchicine before and stopped within 4 weeks after 1st dose of ACZ drug (≤ 4 weeks)

Colchicine positive defined as :

- Patient who took colchicine continuing after receiving 1st ACZ drug
- Patient who took colchicine after 1st dose of ACZ drug and stopped it after 4 weeks (> 4 weeks)

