4.1.4 Criteria applicable for patients with crFMF (cohort 3)

At Screening:

15. Diagnosis of type 1 FMF disease according to Tel Hashomer criteria ([Livneh et al, 1997](#)) but no active flare at the time of screening

16. At least one of the known MEFV gene exon 10 mutations

17. One of the following two:

- a. Documented active disease despite colchicine therapy (from a minimum of 1.5 mg up to 3.0 mg/day or equivalent pediatric age/ weight adjusted dosing regimen depending on Local Guidelines/ standard practice). Patients on current colchicine treatment will continue at stable dose during the study.
- b. Documented intolerance to effective doses of colchicine (from a minimum of 1.5 mg up to 3.0 mg/day or equivalent pediatric age/ weight adjusted dosing regimen depending on Local Guidelines/ standard practice)

18. Historical data showing a frequency of at least 1 attack/month

For patients receiving therapy with biologics, this criterion applies to the last 12 months before they started any therapy with biologics.

At Randomization:

19. Acute crFMF flare characterized by inflammation and serositis in the opinion of the investigator, lasting approximately 12 to 72 hours

20. Active clinical crFMF flare as evidenced by “mild”, “moderate” or “severe” disease activity” (PGA ≥ 2)

21. CRP > 10 mg/L (Normal CRP range ≤ 10 mg/L)

Applicable exclusively for Japanese crFMF patients with non-exon 10 mutations:

At Screening:

22. Criteria #15, #17, #18 as outlined above

23. At least one MEFV gene non-exon 10 mutation

At beginning of Epoch 3:

24. Criteria #19, #20, and #21 as outlined above

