1.9 Concomitant medication

The number and percentage of patients taking prior/concomitant medication will be summarized by cohort, treatment group in each epoch and ATC class for the safety set. The number and percentage of patients with surgeries and medical procedures will be summarized by cohort, treatment group in each epoch and MedDRA preferred term for the safety set. Prior and concomitant medications will be summarized by treatment group in separate tables. Prior medications will be summarized by initial randomized treatment groups in epoch 2. Concomitant medications will be summarized by epoch and treatment groups (defined in [section 1.3](#)). Concomitant medication occurring in follow-up period after discontinuation of study will be listed but not summarized in tables.

Prior medications are defined as treatments taken and stopped prior to first dose of study treatment in epoch 2. Any medication given at least once between the day of first dose of randomized study treatment and the date of the last study visit will be a concomitant medication, including those which were started pre-baseline and continued into the period where study treatment is administered.

Rescue medications (Corticosteroids and NSAIDS) will also be separately summarized by cohort, epoch, initial randomized treatment and treatment sequence (defined in [section 1.3](#)) and ATC class.

Colchicine positive subjects, will be summarized using counts and percentages of subjects who took colchicine at baseline and stopped before or at the end of epoch 2 and subjects who started taking colchicine after day 1 and stopped before or at the end of epoch 2. Subjects will be defined as colchicine positive according to the following:

- Patient who took colchicine continuing after receiving 1st ACZ drug
- Patient who took colchicine after 1st dose of ACZ drug and stopped it after 4 weeks (>4weeks)

Colchicine information for crFMF cohort will be listed.

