1.10 Efficacy evaluation

All efficacy evaluations will be performed on the full analysis set (FAS). For the overall analysis from baseline to epoch 4, patients who randomized to Placebo group at the beginning of epoch 2, only data after the first dose of ACZ885 will be included.

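### The crFMF colchicine subgroups are timed from the first canakinumab dose, so a placebo responder who uses colchicine during the study fits neither group as written

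*SAP*

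**What the plan says.** SAP 1.10.3 states: "Primary and secondary efficacy endpoints based on week 16 will be repeated by Colchicine subgroup as defined below for crFMF cohort only". Under SAP 1.10 these evaluations use the full analysis set, so they compare canakinumab with placebo.

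Five items define the two groups.
- Negative, item 1: "Colchicine Naïve patients (no colchicine before or after treatment".
- Negative, item 2: "Patient who took colchicine before and stopped before receiving ACZ drug".
- Negative, item 3: "Patient who took colchicine before and stopped within 4 weeks after 1st dose of ACZ drug".
- Positive, item 1: "Patient who took colchicine continuing after receiving 1st ACZ drug".
- Positive, item 2: colchicine taken after the first ACZ dose and stopped more than 4 weeks later.

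Only negative item 1 does not refer to ACZ. SAP 1.9 repeats both positive items after the words "Subjects will be defined as colchicine positive according to the following". Protocol 4.1.4, criterion 17a, adds: "Patients on current colchicine treatment will continue at stable dose during the study".

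**The concern.** A subgroup for a between-arm comparison should be fixed before treatment starts and should mean the same thing in both arms. Here, four of the five items are timed from an event that every treated canakinumab patient has on Day 1. A placebo patient has that event only after failing the endpoint. If having the anchor date depends on outcome in one arm, the placebo group within a subgroup can be stripped of its responders.

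Whether canakinumab works with and without background colchicine is an obvious question in colchicine-resistant disease. SAP 1.1 says the Week 16 data form part of the marketing authorization package, so these subgroup tables are likely to be read closely.

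**Working it through.** **1. What ACZ means.** Protocol 1.1 introduces canakinumab as ACZ885. SAP 1.10 and 1.13 say that, in the overall analysis to Epoch 4, patients randomized to placebo contribute only data after their first ACZ885 dose, so for them that dose comes later than Day 1. SAP 1.10.4 speaks of patients initially randomized to ACZ. Where SAP 1.9 means both arms, in defining prior medication, it refers to the first dose of study treatment. The literal reading is canakinumab.

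**2. Which placebo patients have a first ACZ dose.** In Epoch 2 they receive canakinumab only through blinded escape (Day 8 to Day 28) or open-label escape (Day 29 onward): Protocol 3.1.2.2 and 3.1.2.3. Escape is non-response for the primary endpoint (SAP 1.10.1.3) and failure for PGA, CRP and SAA (SAP 1.10.2.1). Placebo patients who complete Epoch 2 without re-flare are withdrawn from study treatment (Protocol 3.1.3.1). So no placebo responder has a first ACZ dose, and every placebo patient who has one in Epoch 2 is a non-responder by rule.

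**3. Applying the five items to a placebo patient who never receives canakinumab.**

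| Colchicine history | Group |
|---|---|
| Never used | Negative, item 1 (few or none, since criterion 17 requires active disease despite colchicine, or intolerance to it) |
| Stopped before Day 1 | Arguably negative, item 2 |
| Used during the study | No item fits |

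The third row matters most, because criterion 17a keeps current users on colchicine.

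**4. Other defects in the items.**
- Overlap: a patient on colchicine at first dose who stops in week 2 meets positive item 1 and negative item 3.
- Gap: a patient who starts after the first dose and stops within 4 weeks meets none.
- Different clocks: suppose colchicine stops on Day 36. A canakinumab patient (anchor Day 1) stopped 36 − 1 = 35 days after the anchor, outside 4 weeks. A placebo patient who escaped on Day 15 stopped 36 − 15 = 21 days after it, inside 4 weeks.

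**5. Size if patients who fit nowhere are left out.** The plan gives no figure for this subgroup. Its enrolment figures reproduce and are not in dispute: 180 / 3 = 60 per cohort, 60 / 2 = 30 per arm, and 180 / (1 − 0.20) = 225 screened. No response rate is visible in the documents, so I assume 10% and 20% on placebo and treat all 30 placebo patients, hence all placebo responders, as on-study users.
- Placebo responders: 0.10 × 30 = 3, or 0.20 × 30 = 6.
- With them removed, the placebo rate is 0/27 or 0/24, which is 0%.
- Inflation = (canakinumab rate − 0) − (canakinumab rate − placebo rate) = placebo rate, so 10 or 20 points. At an assumed 60% against 20%, the risk difference moves from 40 to 60 points.

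As an illustration, I enumerated two binomials exactly, with equal true rates in the arms and a one-sided Fisher test at 2.5%. The last column removes the placebo responders only.

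| Per arm | True rate, both arms | Rejection, all patients | Rejection, placebo responders removed |
|---|---|---|---|
| 30 | 10% | 0.5% | 7.2% |
| 30 | 20% | 1.1% | 50% |
| 15 | 10% | 0.3% | 0.4% |
| 15 | 20% | 0.8% | 5.7% |

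**The case against.** The strongest reply is that ACZ drug is loose wording for first study drug. SAP 1.10.3 sets up two groups with no excluded category, efficacy is analysed on the full analysis set, and SAP 1.10.2.1 says that all randomized Epoch 2 patients count for PGA, CRP and SAA. Just before the ACZ wording, SAP 1.9 frames colchicine use around baseline and Day 1. On that reading every patient has an anchor and the 0% placebo rate never arises. Criterion 17a also means that on-study use should largely match baseline use if the protocol is followed, so only stoppers and new starters would differ.

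Much of this stands. A reader might infer that no placebo responder can be classified and that the comparison is biased. The documents do not support either statement. Negative item 1 needs no ACZ dose and item 2 can be stretched to early stoppers. The bias requires a rule that drops the remaining patients, and the SAP states none.

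The reply does not remove the defect. The text says ACZ, the SAP uses that term for canakinumab elsewhere, and whoever programs the tables must choose a reading. Under the lenient reading, membership still depends on what happened after randomization, and the overlap and the gap remain.

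**Conclusion.** The subgroup definition in SAP 1.10.3 is defective and should be corrected. As written, placebo responders who use colchicine during the study belong to neither group, and having an anchor date in the placebo arm depends on the outcome.

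The size is conditional. If such patients are left out, the placebo rate among classified on-study users is 0% and the risk difference is overstated by up to the placebo response rate. That is 10 to 20 points if the rate is 10 to 20% and all placebo responders are on-study users; both conditions are assumptions. The overstatement is smaller if some responders fall in the negative group, and it vanishes if the anchor is first study drug. The part that remains under that reading, membership decided after randomization, has not been sized and may be small if criterion 17a is followed.

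A reader might also infer that the crFMF primary result or its type I error is at risk. It is not: this is a subgroup repeat in one cohort, outside the H1 to H5 sequence in SAP 1.10.2.1. The rejection rates above show only how far such a table could mislead.

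**What to change.** In SAP 1.10.3, replace the five items with one baseline rule for both arms: colchicine (ATC M04AC01) ongoing on the date of the first study-drug dose (Day 1), yes or no. Every patient in the crFMF full analysis set is then classified once, before any outcome, on the same clock in both arms.

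In SAP 1.9, keep the descriptive counts of on-study use, because a baseline flag cannot show who stopped or started later. Anchor them to the first dose of study treatment instead of ACZ. I ask for no change to the creatinine clearance summary in SAP 1.13.3: it is a safety description, and no bias has been shown there.

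The cost is a few lines of SAP text and simpler programming. The drawback is some misclassification of actual exposure: patients who stop soon after Day 1 stay in the yes group, and those who start after Day 1 stay in the no group. The SAP 1.9 counts will show how many there are.

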1.10.3.1 Additional analyses

Number and percentage of patients with resolution of index flare at day 15 based on status of receiving add-on dose before day 15 will be presented by initial randomized treatment. In addition, number and percentage of responders at day 29 for non-responders at day 15 based on their value at day 15 and by status of up-titration before day 29 will be presented.

1.10.4 Exploratory analysis

An exploratory analysis will be performed where the primary and secondary efficacy analysis on week 16 in the randomized treatment epoch will be repeated on Full Analysis Set where patients initially randomized to ACZ will be considered as responder if : Resolution of index flare at day 15 and no flare after day 15 or for those who have been up-titrated to 300 mg before day 29, have resolution of index flare at day 29 (PGA < 2 and CRP within normal range (≤ 10 mg/L) or reduction of $\geq 70\%$ from baseline) and no flare after day 29.

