3.1.2 Randomized treatment epoch (Epoch 2)

3.1.2.1 Randomization

At baseline, eligible patients will be randomized in a ratio of 1:1 within each cohort to one of below 2 treatment arms:

- Canakinumab 150 mg (or 2 mg/kg for patients weighing ≤ 40 kg) every 4 weeks (q4w)
- Placebo

Patients from the non-randomized group will enroll to the open label arm of canakinumab 150 mg (or 2 mg/kg for patients weighing ≤ 40 kg) every 4 weeks (q4w). They will be eligible for add-on injection and up-titration as described in the following sections but always receive open label medication.

All patients will receive the first subcutaneous injection at Baseline and will return to the site every 4 weeks to receive additional injections of investigational treatment for 16 weeks.

The resolution of the index flare will be assessed at Day 15. Resolution of the index flare is defined as PGA <2 (“minimal” or “none”), **and** CRP within normal range (≤ 10 mg/L) or reduction by at least 70% from baseline. Patients whose index flare has resolved will not be up-titrated. If their index flare has not resolved by Day 15, they will be eligible for blinded escape (see [Section 3.1.2.2](#)).

Visits to assess efficacy and safety are scheduled at Day 15, Day 29 and subsequently at 4 weeks intervals during the randomized treatment epoch. Patients might receive an up-titration if they have persistent disease activity or they re-flare before Day 29 (see [Section 3.1.2.2](#)) or after Day 29 (see [Section 3.1.2.3](#)).

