3.1.2.2 Blinded escape (non-resolution/ early re-flare before Day 29)

The assignment to blinded escape will be managed by the IRT.

Patients whose index flare has not resolved by Day 15 will be eligible for blinded escape.

If patients experience persistent “mild”, “moderate” or “severe” disease activity (i.e., PGA ≥ 2 [clinical flare]), or CRP persistent >10 mg/L with less than 40% reduction from baseline from Day 8 to Day 14, they will also be eligible for blinded escape at an unscheduled visit.

In case one of the conditions described above occurs, patients will receive a single add-on s.c. injection of canakinumab (150 mg s.c. [or 2 mg/kg for patients ≤ 40 kg]) from Day 8 to Day 28 but will not be unblinded to their randomized treatment (see [Table 3-1](#)). This will lead to blinded up-titration to the next dosing regimen according to the initial randomized treatment and will be initiated from Day 29 onward through IRT.

- Patients randomized to canakinumab 150 mg q4w will receive 2 injections of canakinumab on Days 29, 57 and 85 equaling to a canakinumab 300 mg q4w regimen
- Patients randomized to placebo will receive 1 injection of canakinumab and 1 injection of placebo each on Days 29, 57 and 85 equaling to a canakinumab 150 mg q4w regimen

If the patient’s condition is not improving after add-on injection, rescue medication should be used from Day 15 until treatment is administered at Day 29. All patients on blinded escape will be followed-up for efficacy and safety.

Non-randomized cohort

Canakinumab naïve Japanese crFMF patients with non-exon 10 mutations or patients >28 days but <2 years old will initiate open-label treatment receiving canakinumab 150 mg (or 2 mg/kg for patients weighing ≤ 40 kg) q4w at Day 1. Index flare resolution will be assessed at Day 15.

Patients experiencing persistent “mild”, “moderate” or “severe” disease activity (i.e., PGA ≥ 2 [clinical flare]), or CRP persistent >10 mg/L with less than 40% reduction from baseline from Day 8 to Day 28 can receive a single add-on s.c. injection of canakinumab (150 mg s.c. [or 2 mg/kg for patients ≤ 40 kg]). If the patient’s condition is not improving after add-on injection, rescue medication should be used until the patient’s next visit at Day 29 when study treatment will be administered.

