3.1.2.3 Open label treatment arm (re-flare on/ after Day 29)

If on Day 29 or after Day 29, patients still have “mild”, “moderate” or “severe” disease activity (PGA ≥ 2 [clinical flare] and CRP ≥ 30 mg/L [serological flare]), up-titration to the next dosing regimen is allowed and patients will initiate open label escape at the next scheduled visit including Day 29 (see [Table 3-1](#)).

The following up-titration will be initiated at the next scheduled visit based on the IRT information:

- Patients randomized to placebo will receive canakinumab 150 mg q4w. If they still have “mild”, “moderate” or “severe” disease activity (PGA ≥ 2 [clinical flare] and CRP ≥ 30 mg/L [serological flare]) or re-flare at the next scheduled visit, they will increase the dose to canakinumab 300 mg q4w
- Patients randomized to canakinumab 150 mg q4w will increase the dose to canakinumab 300 mg (or 4 mg/ kg for patients weighing ≤ 40 kg) q4w

Table 3-1 Criteria for add-on injection or up-titration in Epoch 2

	PGA criteria	CRP criteria	Treatment option	IRT update
Day 8 to 14	Persistent PGA ≥ 2 OR	CRP persistent >10 mg/L with less than 40% reduction from baseline	Add-on injection allowed	Blinded up-titration effective at next scheduled visit (Day 29)
Day 15	PGA ≥ 2 OR	CRP >10 mg/L and no reduction by at least 70% from baseline	No Index flare resolution* Add-on injection allowed (only if add-on injection was not received earlier)	Blinded up-titration effective at next scheduled visit
Day 16 to 28	PGA ≥ 2 OR	CRP >10 mg/L and no reduction by at least 70% from baseline	Add-on injection allowed (only if add-on injection was not received earlier)	Blinded up-titration effective at next scheduled visit
Day 29 to 112	PGA ≥ 2 AND	CRP ≥ 30 mg/L	Up-titration allowed	Open label up-titration effective at next scheduled visit including Day 29 visit

* For patient with index flare resolution at Day 15, criteria defined for Day 29 will be applied

Single Add-on injection is allowed only once in Epoch 2

For patients who already received blinded escape prior to Day 29 and require a second up-titration:

- Patients randomized to placebo *who received blinded escape* (150 mg q4w) *prior to Day 29* will receive open-label canakinumab 300 mg q4w
- Patients randomized to canakinumab 150 mg q4w *who received blinded escape* (add on 150 mg q4w) *prior to Day 29* must not further up-titrate

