1.10.1.3 Handling of missing values/censoring/discontinuations

Patients needing dose escalation in the canakinumab arms, or who escape from placebo to canakinumab in the randomized treatment epoch (Epoch 2), or discontinued from the study due to any reason prior to evaluating the primary endpoint will be considered as non-responders in epoch 2.

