1.10.2.1 Testing strategy

The following hypotheses will be included in the closed testing procedure, and type-I-errors will be set such that a family-wise type-I-error rate of 2.5% is kept (one sided tests)

- Primary objective: H_1 .

Secondary objectives:

- H_2 : Canakinumab 150mg q4w is not different to placebo with respect to the percentage of patients with PGA < 2 at Week 16.
- H_3 : Canakinumab 150mg q4w is not different to placebo with respect the percentage of patients with CRP ≤ 10 mg/L at Week 16.
- H_4 : Canakinumab 150mg q4w is not different to placebo with respect the percentage of patients with SAA ≤ 10 mg/L at Week 16.
- H_5 : Canakinumab 150mg q8w is not different to placebo with respect to the percentage of responders (absence of new flares) at Week 40.

If the primary objective is achieved, all secondary endpoints in the randomized treatment epoch (Epoch 2) will be assessed. If all secondary objectives are achieved in the randomized treatment epoch (Epoch 2), then the secondary objective in the randomized withdrawal epoch will be tested. The 95% confidence interval for the proportions will be calculated using exact (Clopper-Pearson) method.

Physician's global assessment of disease activity (PGA)

PGA is based on a 5-point scale for disease associated signs and symptoms:

0 (=none/no), 1 (=minimal), 2 (=mild), 3 (=moderate), and 4 (severe).

Frequency tables will be provided by analysis visit and randomized treatment groups for each cohort. Between-treatment differences for the proportion of patients with $\text{PGA} < 2$ at Week 16 will be analyzed using a logistic regression model with treatment group, and baseline PGA as explanatory variables for each cohort. All randomized patients at start of Epoch 2 will be considered for this analysis. Patients needing dose escalation in the canakinumab arms, or who escape from placebo arms to canakinumab in the randomized treatment epoch (Epoch 2), or discontinued from the study due to any reason prior evaluating the endpoint at week 16, will be considered as having $\text{PGA} \geq 2$. If the logistic regression model has difficulty converging due low or high response rates, then Firth's method will be used in the logistic regression model. If the convergence issue is still not resolved then Canakinumab treatment group will be compared to placebo with respect to the proportion of patients with $\text{PGA} < 2$ at Week 16 will be analyzed using the Fisher's exact test.

Serological remission

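### If up-titration before Day 29 means blinded escape, the exploratory re-analysis in SAP 1.10.4 gives only the canakinumab arm a second route to response, so its Week 16 comparison with placebo favours canakinumab even for an inert drug.

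*SAP*

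**What the plan says.** SAP 1.10.4 repeats the primary and secondary Week 16 analyses on the Full Analysis Set with a changed responder definition: "patients initially randomized to ACZ will be considered as responder if" they meet the usual Day 15 definition or, "for those who have been up-titrated to 300 mg before day 29, have resolution of index flare at day 29", followed by no flare. It states no rule for patients randomized to placebo.

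The standing rules are elsewhere. For the primary endpoint, SAP 1.10.1.1 and 1.10.1.3 count as non-responders the canakinumab patients who need dose escalation and the patients "who escape from placebo to canakinumab in the randomized treatment epoch". For PGA at Week 16, SAP 1.10.2.1 imputes failure both to canakinumab patients needing escalation and to patients "who escape from placebo arms to canakinumab in the randomized treatment epoch (Epoch 2), or discontinued". The CRP and SAA rules there have the same form.

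Protocol 3.1.2.2 and Table 3-1 set one set of blinded-escape criteria for both arms. The add-on injection falls on Day 8 to 28 and leads to "blinded up-titration to the next dosing regimen according to the initial randomized treatment and will be initiated from Day 29 onward through IRT". On that path placebo patients move to a 150 mg q4w regimen, so they cannot meet the 300 mg condition.

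**The concern.** Take two patients with the same course: unresolved at Day 15, add-on given, resolved at Day 29, no later flare. Under SAP 1.10.4 the one randomized to canakinumab is a responder and the one randomized to placebo is not. Part of any difference in that table would then come from the scoring rule and not from the drug.

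What is at stake is how this one analysis is read. SAP 1.1 says that the Week 16 data go into the marketing authorization package. A risk difference, odds ratio and p-value that rest on two response definitions could mislead there.

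**Working it through.** **1. What up-titrated before Day 29 can mean.** Read literally against Protocol 3.1.2.2, only the add-on comes before Day 29 and the new regimen starts on Day 29. The group is then empty and the analysis repeats the primary one. Other text treats blinded escape itself as the up-titration. Protocol 3.1.2.1 says "Patients might receive an up-titration if they have persistent disease activity or they re-flare before Day 29" and refers to the blinded-escape section. Protocol 3.1.2.3 speaks of patients "who already received blinded escape prior to Day 29 and require a second up-titration". SAP 1.10.3.1 plans a Day 29 table "by status of up-titration before day 29 will be presented", and SAP 1.10.5 plans a CRP table for the same group. Blinded escape is therefore the better supported reading, and the steps below use it.

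**2. Expected difference for an inert drug.** Let r be the chance of response by the Day 15 route, equal in both arms.

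- Placebo rate = r, because escapers are non-responders.
- Canakinumab rate under SAP 1.10.4 = r + e × s.
- Expected risk difference = e × s, which exceeds zero whenever any escaper resolves by Day 29 and stays flare-free.

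**3. Inputs.**

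- Sample size: 30 per arm per cohort (Protocol 4). The plan's own figures agree: 3 × 2 × 30 = 180 randomized, and 180 / (1 − 0.20) = 225 screened.
- Test: Fisher's exact, one-sided 2.5% within each cohort (SAP 1.10.1.2).
- Minimum entry flare rates (Protocol 4.1.2 to 4.1.4): more than 6 a year for recurrent TRAPS, at least 3 in 6 months for HIDS (6 a year), and at least 1 a month for crFMF (12 a year).
- Assumed, because the documents do not give them: e = 40–60%; f, the share of escapers resolved at Day 29, = 25%, 50% or 100%; Poisson flares at a constant rate; only non-escapers can respond by the Day 15 route.

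**4. Formulas.** The chance of no flare is exp(−rate × days / 365.25), over 84 days (Day 29 to 113) or 98 days (Day 15 to 113). Then r = (1 − e) × q98 and s = f × q84.

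Example at 6 a year, e = 40%, f = 50%:

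- q84 = exp(−6 × 84 / 365.25) = 0.2516 and q98 = exp(−6 × 98 / 365.25) = 0.1999.
- r = 0.6 × 0.1999 = 0.1199.
- e × s = 0.4 × 0.5 × 0.2516 = 0.0503.
- The arms compare at 12.0% and 17.0%. Exact enumeration of all 31 × 31 outcomes gives rejection in 3.2%.

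**5. Results for an inert drug** (bias in points, then rejection rate):

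| Flares/year | e | r | f = 25% | f = 50% | f = 100% |
|---|---|---|---|---|---|
| 6 | 40% | 12.0% | 2.5; 1.6% | 5.0; 3.2% | 10.1; 9.6% |
| 6 | 60% | 8.0% | 3.8; 1.7% | 7.5; 5.4% | 15.1; 22.6% |
| 8 | 40% | 7.0% | 1.6; 0.5% | 3.2; 1.2% | 6.4; 3.7% |
| 8 | 60% | 4.7% | 2.4; 0.4% | 4.8; 1.6% | 9.5; 8.3% |
| 10 | 40% | 4.1% | 1.0; 0.1% | 2.0; 0.3% | 4.0; 1.0% |
| 10 | 60% | 2.7% | 1.5; 0.1% | 3.0; 0.3% | 6.0; 2.0% |

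At 12 a year with f = 100%, the bias is 2.5 points (e = 40%) or 3.8 points (e = 60%), with rejection in 0.15% or 0.30%. With the same rate in both arms, rejection is at most 1.37% at any rate. At r = 8% the rejection rate passes 2.5% once e × s exceeds about 4.9 points, and at r = 12% once it exceeds about 4.2 points.

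**6. PGA, CRP and SAA.** SAP 1.10.2.1 imputes failure to escalated canakinumab patients as well as to placebo escapers. SAP 1.10.4 redefines a responder on the flare composite and does not say whether that imputation is lifted. If it stands, both arms are treated alike. If it is lifted for canakinumab alone, the same bias appears. The text does not settle which.

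**The case against.** The strongest reply is that little hangs on this analysis. It is labelled exploratory, has no alpha and lies outside H1–H5. Protocol 1.2 names dose individualization as a purpose of the study, so response after up-titration is worth showing. This stands and limits the point to a minor one. It justifies describing the canakinumab arm, but not testing it against a placebo arm scored by a stricter rule.

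Other analyses help in part. The third sensitivity analysis in SAP 1.10.1.5 re-scores add-on patients with no restriction to one arm, but covers only add-ons before Day 15. The text of SAP 1.10.3.1 does not limit its Day 29 table to canakinumab patients. The primary result is reported as well, so the contribution of the second route can be found by subtraction.

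The size is also open to challenge. The largest figures need every escaper on an inert drug to resolve by Day 29, at the lowest flare rate that entry allows. Inflation above 2.5% disappears at 8 a year unless more than half of the escapers resolve, and at 10 a year in every case shown. This stands too. Flares missed between visits would raise s and push the other way.

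A reader might infer that the PGA, CRP and SAA re-analyses are biased as well. The documents do not support that, because the failure imputation for canakinumab escalation is not stated to be lifted.

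**Conclusion.** On the blinded-escape reading, the primary re-analysis in SAP 1.10.4 is biased toward canakinumab. The direction follows from the rule. The size rests on assumed escape and resolution shares and a Poisson flare model. For e = 40–60% and a quarter to all escapers resolved at Day 29, the bias at 6 flares a year is 2.5–15.1 points with 1.6–22.6% rejection. Rejection is 0.4–8.3% at 8 a year and at most 2.0% at 10 a year or more. Chronic TRAPS patients have no entry flare frequency and are not covered.

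On the literal reading the group is empty and the analysis adds nothing. Either way the sentence needs correcting. The PGA, CRP and SAA re-analyses are unspecified.

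A reader might infer that the trial's primary conclusion or its type I error is affected. It is not: the primary analysis treats escapers in both arms as non-responders, and SAP 1.10.4 does not feed the testing hierarchy. The point is minor.

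**What to change.** Preferably, report the canakinumab-arm proportion under this definition with its Clopper-Pearson interval, and give no test, odds ratio or risk difference against placebo. If a comparison is kept, apply the same Day 29 rule to both arms, label it a comparison of starting strategies, and note that placebo escapers received canakinumab.

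In either case:

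- Name the recorded event that opens the second route, for example an add-on injection on Day 8 to 28, so that the sentence agrees with Protocol 3.1.2.2 and Table 3-1.
- State the rule for placebo patients.
- State how the definition applies to PGA, CRP and SAA, and whether the failure imputation for escalation stays in force in each arm.

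This changes SAP wording only. The first option loses an exploratory p-value. The second dilutes the contrast, because placebo patients are credited with responses after receiving canakinumab.
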